Pre Rest + SLR: After identifying the appropriate angle/height to induce a 2-point pain increase, patients will lie in the supine position and will be instructed to “rest with your eyes closed” for 5 minutes. VAS pain ratings will then be collected. With the aid of a technician, patients will then lift their legs to the angle/height calibrated to produce a 2-point VAS pain increase. After 5 minutes, we will collect pain ratings.

Post Rest + SLR: We will wait 10 minutes before continuing the study to control for the time spent administering the drug/saline bolus take effect. VAS pain ratings will be collected after 10 minutes. We will then match the procedures employed in Pre-Rest + SLR.

Post Rest + Heat: A thermal probe will be placed on the back of the “unaffected” calf while patients lie in the supine position. They will be instructed to “rest with your eyes closed” for 8 minutes. We will then match the procedures employed in Pre Rest + Heat.

Patient Randomization:

After successful completion of session 1, participants will be randomized to their respective group. Randomization will be tracked in the Screening/Enrollment Log that is maintained by the clinical

coordinator. Randomization will be stratified so that each sex will have their respective list of randomization codes. Males and females will be randomized without replacement across a block of 60 codes using an Excel-based random number generator. Male and female participants will be randomized within three days of their respective scheduled psychophysical training session. The two treatment arms (mindfulness meditation = A; non-mindfulness meditation =B) will be permuted with respect to treatment assignment, in a double-blind fashion, respectively. We will employ a similar randomization procedure within each group to determine when (i.e., Session 6 or 7) each participant will receive naloxone and saline in a crossover manner.

Sessions 2-5: Regimen:

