Drug Administration: All studies will be conducted with the supervision of ACTRI nurses in the ACTRI. As previously conducted (Zeidan, Adler-Neal et al. 2016), a 0.15mg/kg bolus dose of naloxone (Naloxone HCl, Amphastar Pharmaceuticals) or 25ml of normal saline will be administered over 10 minutes via the IV line of the antecubital vein of the non-dominant arm. Onset of naloxone-induced opioidergic antagonism occurs within 2 min of infusion and exhibits an average half-life of 64 min (Ngai, Berkowitz et al. 1976). To further ensure that naloxone will antagonize opioid receptors for the study entirety, we will administer a supplementary maintenance intravenous infusion dose of 0.15 mg/kg/h naloxone or saline immediately after bolus infusion ceases. The duration of the study from the onset of IV infusion to completion will be no more than 25 (average time of infusion = approx. 15 minutes). Only the study physicians, research pharmacist, and study coordinator will be aware of participant drug assignment.

Sample Size Determination & Power:

Assuming a conservative 20% dropout rate, we will recruit and randomize a total of 74 cLBP patients (n=37/group) to a mindfulness meditation or non-mindfulness meditation regimen. To conduct group comparisons among the two primary outcomes (naloxone + saline induced changes in pain intensity + unpleasantness) and to ensure an overall type I error rate < 0.05, we used conservative Bonferroni corrections (p= .025) in all power calculations. Employing the pilot data corresponding to preliminary findings and our previous work [22], we fit repeated measures ANOVA models that include indicator variables for group (mindfulness vs. non-mindfulness), drug (naloxone vs. saline), and session order. The estimated square root of mean square errors is 0.23 and 0.30 for pain intensity and pain unpleasantness, respectively. Thirty participants per group will provide 80% power to detect a group difference of 0.19 for pain intensity and 0.24 for pain unpleasantness. Such effect sizes are consistent with those observed from our pilot data. Statistical power will be also greater when pre-regimen pain ratings are entered as covariates to reduce residual variance.

Data Analyses and Interpretation:

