Primary Outcome: Age and sex will be entered as covariates in all appropriate analyses if between group differences exist. To test study hypotheses, a 2 (group) X 2 (rest vs. manipulation) X 3 (naloxone vs. saline) repeated measures (RM) ANOVA will be employed. Post-hoc paired samples t-tests (in each group) will be conducted to test the hypotheses that non-mindfulness meditation but not mindfulness induced analgesia will be reversed by administration of naloxone but not saline.

Exploratory analyses may be conducted (in supplementary papers) on the psychological assessments (Questionnaires for Study Assessments) to better appreciate the relationship in dispositional pain and the potential changes in pain responses due to the respective interventions.

Inclusion of Women and Minorities: Participants will include all sexes and races. We plan to screen from over 2500 cLBP patients from the ACTRI's pain recruitment service, 11 separate providers, and the local community. Based on the latest San Diego-based demographic consensus, we plan to recruit 60% White, 16% Asian, 7% Black, 0.5% Native American, 0.5% Pacific Islander, 12% Other race, 5% two or more races (We expect that 29% of our participants will be Hispanic or Latino). If necessary to obtain minority representation, under-represented racial groups will be targeted specifically for recruitment.

General Considerations:

Data for all individual participants randomized or exposed to study drug will be presented in data listings. Continuous data will be summarized using the following descriptive summary statistics: the number of subjects (n), mean, SD, SE, median, minimum value (min), and maximum value (max). Categorical data will be summarized using counts and percentages.

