10. HUMAN SUBJECTS

Total number of subjects to be enrolled at UCSD

Our targeted sample size is 60 cLBP (30/group). We have exhibited a relatively low attrition rate on previous work, thus we request permission to enroll 74 participants with the goal of retaining 60 participants.

Age: Age will range between 18 and 65 years.

Sex: We will have equal males and females in each group. Groups will be matched by age and sex (15 males/15 females).

Ethnic background: We will include all ethnicities.

Health status: Participants must have a chronic low back pain diagnosis.

All study participants will be recruited from the ACTRI and the local community. We will employ our NIH-approved exclusion and inclusion criteria delineated in previous studies examining cLBP [27; 37; 42] as described below.

Eligibility Criteria: Patients will qualify for the study if medical evaluation demonstrates chronic low back pain that is evoked by lifting the legs. Existing medical records, per physician discretion and low back examinations will confirm diagnosis. Study physicians will confirm diagnosis (Fardon 2001, Wasan, Davar et al. 2005, Jamison, Ross et al. 2010, Wasan, Loggia et al. 2011, Fardon, Williams et al. 2014).

Inclusion criteria include those who:

- a) are between 18-65 years old;
- b) have ongoing chronic pain (pain intensity ≥ 3 on a 0-10 VAS);
- c) have radicular pain for at least 3 months;
- d) are not using other pain management procedures (i.e. CBD oil products) during the study period;
- e) are not taking opioids;
- f) if female and of a child bearing potential age, are not pregnant or nursing mothers;
- g) have not had back surgery within a year of the study start date;
- h) lack sensory/motor deficits that preclude participation in pain-inducing procedures;
- i) have no meditation experience;
- j) are straight leg raise test positive
- k) do not have any known allergies to naloxone or similar drugs

l) do not have a history of syncope and/or fear of needles/blood.

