#### Exploratory outcome

- SF-12 Health Survey (SF-12): This is a 12-item version of the SF-36 item Health Survey designed to assess general mental and physical functioning, and overall health-related quality of life.

**Statistical Analysis Plan:** To test the primary hypotheses, a 2 (group) X 2 (rest vs. manipulation) X 3 (baseline vs. naloxone vs. saline) mixed model ANOVA will be employed to test differences in the change in pain from supine to straight leg raise test (SLR 1; SLR 2) within and across each testing session. Significant interactions will be explored using post-hoc paired simple effects tests to test the hypotheses that non-mindfulness meditation but not mindfulness induced analgesia will be reversed by administration of naloxone but not saline. Between group comparisons will also be explored with simple effects tests.

Secondary and exploratory outcomes will be assessed with a 2 (group) X 2 (baseline vs. post-intervention) by testing between and within group differences comparing baseline vs. post-study assessments. Simple effects tests will interpret significant main effects and interactions.

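### Sex is a randomisation stratum, yet sex and age enter the model only if the groups happen to differ; sex would almost always be left out, at a conservative cost in power

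*Protocol*

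**What the plan says.** - **Covariate rule** (protocol section 9, Data Analyses and Interpretation): "Age and sex will be entered as covariates in all appropriate analyses if between group differences exist". The text does not say what counts as a difference, when it is judged, or which analyses are appropriate.
- **Primary model in the protocol** (same paragraph): "a 2 (group) X 2 (rest vs. manipulation) X 3 (naloxone vs. saline) repeated measures (RM) ANOVA will be employed". Age and sex are not terms in it.
- **Randomisation** (protocol section 9, Patient Randomization): "Randomization will be stratified so that each sex will have their respective list of randomization codes", and "Males and females will be randomized without replacement across a block of 60 codes using an Excel-based random number generator".
- **Planned composition** (protocol section 10): "Groups will be matched by age and sex (15 males/15 females" in each group. The randomisation text has a mechanism for sex only, none for age.
- **SAP** (Statistical Analysis Plan paragraph): "2 (group) X 2 (rest vs. manipulation) X 3 (baseline vs. naloxone vs. saline) mixed model ANOVA will be employed". No covariate is named for the primary, secondary or exploratory outcomes, so the SAP neither repeats nor withdraws the protocol's rule.

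**The concern.** In a randomised trial, baseline differences between arms arise by chance. Whether age or sex differs between arms says nothing about whether it predicts pain, and prediction is the reason to adjust. The rule therefore selects covariates on the wrong criterion, and it works differently for the two variables.

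For sex, stratified randomisation removes the imbalance that the rule looks for, so the factor used to randomise is left out of the analysis. If sex predicts pain, its variance stays in the residual while the design has already taken it out of the group comparison. The reported standard error is then larger than the true one.

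For age, entry depends on a chance imbalance and on a threshold that is not written down. Protocol section 4 places both unblinding and analysis after data collection. The check needs group labels, so nothing in the text stops the choice being made with outcomes in hand.

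At stake is precision in comparisons of pain level between the groups, and a model that is fixed in advance and identical in both documents.

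**Working it through.** **1. The plan's own power figure.** Inputs from protocol section 9, Sample Size Determination & Power: 30 per group; differences of 0.19 (intensity) and 0.24 (unpleasantness); root mean square errors of 0.23 and 0.30, taken here as between-person SDs; and "we used conservative Bonferroni corrections (p= .025) in all power calculations", taken as two-sided, so z = 2.241.

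Power = Φ(Δ / (SD·√(2/n)) − z).

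- Intensity: 0.23 × √(2/30) = 0.0594; 0.19/0.0594 = 3.199; 3.199 − 2.241 = 0.958; power 83.1% (81.3% with the noncentral t).
- Unpleasantness: 0.30 × √(2/30) = 0.0775; 0.24/0.0775 = 3.098; 3.098 − 2.241 = 0.857; power 80.4% (78.5% with the noncentral t).

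The stated 80% is approximately reproduced with no covariate in the calculation.

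**2. How often the rule admits each variable.** The protocol gives no threshold, so p < 0.05 is assumed. Simulation: 60 people, 30 per sex, 8,000 trials per scenario.

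- Sex: 0% of trials with exact 15/15 balance; about 0.6% when 30 per sex are drawn from a 60-code list.
- Age: about 5%, which is the level of the test.

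**3. Effect of omitting a balanced stratum.** Let R² be the share of variance in the analysed outcome explained by sex. The documents give no value, so the range is assumed. With sex balanced, the true standard error of the group difference is SD·√(1−R²)·√(2/n), while the model without sex reports SD·√(2/n).

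- Overstatement of the standard error: 1/√(1−R²)
- True type I error: 2·(1 − Φ(2.241/√(1−R²)))
- Power without sex: Φ((3.199 − 2.241)/√(1−R²))
- Power with sex: Φ(3.199/√(1−R²) − 2.241)

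| R² for sex | Model SE too large by | True type I error (nominal 0.025) | Power without sex | Power with sex |
|---|---|---|---|---|
| 0 | 0% | 0.0250 | 83.1% | 83.1% |
| 0.05 | 2.6% | 0.0215 | 83.7% | 85.1% |
| 0.10 | 5.4% | 0.0181 | 84.4% | 87.1% |
| 0.20 | 11.8% | 0.0122 | 85.8% | 90.9% |

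The power columns use the intensity inputs from step 1 and the normal approximation.

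**4. The conditional rule against its alternatives** (same simulation, exact sex balance; Monte Carlo error about 0.002 for type I error and 0.004 for power).

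| Sex and age each explain | Quantity | Never adjust | Conditional rule | Always adjust |
|---|---|---|---|---|
| 10% | Type I error | 0.0195 | 0.0181 | 0.0256 |
| 10% | Power | 82.3% | 82.6% | 88.6% |
| 0% | Power | 81.1% | 80.9% | 80.4% |

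The conditional rule behaves almost like no adjustment.

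**5. Net effect of always adjusting for both.** The formula √(1−R²) ignores the price of chance age imbalance. In 20,000 simulated trials per value, with R² now the joint share split equally between sex and age, the net reduction in standard error was 1.7%, 4.4% and 9.9% at R² = 0.05, 0.10 and 0.20. The formula gives 2.5%, 5.1% and 10.6%. At R² = 0, adjusting raised the standard error by 0.9%.

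**6. Which tests are touched.** A sex or age effect that adds the same amount to every rating of a person cancels from any within-person difference. In one illustrative mixed model with an additive sex effect, adding sex lowered the standard error of the group effect (there, the group difference under saline) from 0.0728 to 0.0701. The standard error of group by drug stayed at 0.0752.

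**The case against.** The strongest reply is that the main hypotheses are not affected. They rest on paired naloxone-saline tests within each group and on the group by drug interaction, from which an additive sex or age effect cancels. The same holds for group by rest/manipulation. It also holds for the SAP's secondary analyses, which test group by baseline/post-intervention. The SAP frames the primary test on the change from supine to leg raise, and leg height is calibrated to each person, which may further reduce sex- or age-related spread. All of this stands. What remains is the group main effect and group comparisons at one time point. If the protocol's 0.19 and 0.24 refer to differences in change scores, R² for sex on that scale is nonzero only if sex modifies the change, and it may be near zero.

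A second reply is that the SAP of May 3, 2023 fixes a model with no covariates, so nothing is chosen from the data. If the SAP governs, the data dependence disappears, but the stratum is then never in the model. The SAP does not say that it replaces the protocol's rule, so the two still need reconciling.

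A reader might infer three stronger things that the documents do not support:

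- **The rule raises the false-positive rate.** It does not. Type I error under the conditional rule was 0.0181 in the 10% scenario, below 0.025.
- **The trial is underpowered because of it.** The stated 80% is approximately reproduced with no adjustment.
- **All group comparisons and secondary outcomes lose precision.** Those based on within-person change do not, unless sex or age modifies the change.

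**Conclusion.** The point holds, with limited reach. As written, the rule would almost always leave out sex, the one factor the trial stratifies on, and would admit age in about 1 trial in 20 for a reason unrelated to its value as a covariate. The SAP is silent on both.

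If sex is prognostic, the model standard error of the group main effect and of single-time-point group comparisons is too large by 2.6% to 11.8% for an assumed R² of 0.05 to 0.20, and by nothing at R² = 0. On the intensity inputs, adding sex gains about 1.4 to 5.1 percentage points of power over that range (85.1 − 83.7 and 90.9 − 85.8). The error is in the conservative direction.

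This rests on assumed R² values, two-sided alpha, root mean square error used as the between-person SD, near-exact sex balance, a 5% balance test and additive covariate effects. The reading of the text is secure; the size is conditional. This is a cheap improvement that should be made, not a threat to the validity of the naloxone hypotheses.

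**What to change.** Delete the condition on observed group differences. State in both the protocol and the SAP: sex (randomisation stratum) and age are included as fixed covariates in all between-group analyses, regardless of observed balance. Add the same two terms to the SAP's model statement so that the documents agree.

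Cost: one sentence in each document and two degrees of freedom. Both variables are already collected. If neither predicts pain, the standard error is about 1% larger, and simulated power for the intensity comparison is 80.4% instead of 81.1%.

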**Title:** Chronic Low Back Pain and Meditation

**NCT Record #:** NCT04034004

**Date:** May 3, 2023

**PI:** [name]

**Sample Size Determination:** Our targeted sample size is 60 cLBP patients (30/group). To conduct group comparisons among the two primary outcomes (naloxone + saline induced changes in pain ratings) and to ensure an overall type I error rate  $< 0.05$ , we used conservative Bonferroni corrections in all power calculations. Employing the pilot data corresponding to our previous work (Wells et al., 2020), we fit repeated measures ANOVA models that include indicator variables for group (mindfulness vs. non-mindfulness) and session (baseline vs. naloxone vs. saline). The estimated square root of mean square errors is 0.23 (23%) for pain ratings. Thirty subjects will provide 80% power to detect a pain rating difference of 22% between the naloxone and saline conditions in the non-mindfulness group with an estimated SD of 0.3 (30%). We expect no meaningful differences in pain reductions between naloxone and saline infusion during mindfulness meditation. Thus, we will have 80% power to detect a significant group X drug type interaction. Finally, 30 subjects/group will provide 80% power to detect a significant group difference of 19% for pain intensity. Such effect sizes parallel those observed in our pilot data (Wells et al., 2020).

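### Drug order (naloxone in Session 6 or Session 7) is randomised, but the primary models and the paired follow-up tests have no period term (minor; cheap to improve)

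*Protocol*

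**What the plan says.** Protocol section 9, Patient Randomization, sets up the crossover: "We will employ a similar randomization procedure within each group to determine when (i.e., Session 6 or 7) each participant will receive naloxone". The protocol's primary analysis (section 9, Data Analyses and Interpretation) is "a 2 (group) X 2 (rest vs. manipulation) X 3 (naloxone vs. saline) repeated measures (RM) ANOVA will be employed". Its follow-up is "Post-hoc paired samples t-tests (in each group) will be conducted".

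The SAP (Statistical Analysis Plan paragraph) states "a 2 (group) X 2 (rest vs. manipulation) X 3 (baseline vs. naloxone vs. saline) mixed model ANOVA will be employed", applied to the "change in pain from supine to straight leg raise test (SLR 1; SLR 2) within and across each testing session". Significant interactions are then followed by paired simple-effects tests.

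Neither model nor either set of follow-up tests names period, order or sequence. The SAP's sample-size text does have a factor called session, but its levels are given as "session (baseline vs. naloxone vs. saline", so it is drug condition and not calendar order. Session order is named once, in the model fitted to pilot data under Sample Size Determination & Power in protocol section 9. The parallel sample-size texts earlier in section 9 and in the SAP leave it out.

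**The concern.** The naloxone-saline contrast within each group, and its difference between groups, is the mechanistic test of the trial. Session 7 repeats Session 6 a few days later, so responses could shift between the two for reasons unrelated to drug, such as familiarity, practice or expectation. An unadjusted paired difference contains that shift with one sign for participants who get naloxone first and the opposite sign for those who get it second. With equal numbers in the two orders the shift averages out of the estimate but inflates its variance. With unequal numbers part of it stays in the estimate. The trial randomises order and therefore has the information to remove the shift, but the written analysis does not use it.

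**Working it through.** **Inputs from the documents.** n = 30 per group; drug effect 0.22 with SD 0.30 (protocol section 9 and SAP, sample-size texts); alpha 0.025 by Bonferroni (protocol section 9), taken as two-sided because sidedness is not stated. The documents do not say whether 0.30 is the SD of one rating or of the naloxone-saline difference.

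**The plan's own figure.** The plan claims 80% power for 0.22 with 30 participants. A paired t-test at alpha 0.025 gives 94.5% if 0.30 is the SD of the difference. It gives 68.3% if 0.30 is the SD of one rating and the two conditions are uncorrelated (SD of difference 0.30 x sqrt(2) = 0.424). The 80% lies between these. The illustration uses 0.30 and reports 0.424 alongside.

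**Assumed quantity.** Let P be the mean Session 7 minus Session 6 shift in the analysed change, unrelated to drug, that is left after any within-session pre-drug control. The documents give no value; 0.10 and 0.20 are used. The larger is nearly the whole drug effect.

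**Formulas.** Let n1 participants receive naloxone in Session 7 and n2 in Session 6, with n = n1 + n2, drug effect D and SD of the difference s. The naloxone-saline difference has mean D + P in the first set and D - P in the second.

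- Unadjusted mean = D + P x (n1 - n2)/n, so bias = P x (n1 - n2)/n.
- Unadjusted variance of one difference at equal orders = s² + P². With s = 0.30 the SD becomes sqrt(0.09 + 0.01) = 0.316 at P = 0.10, and sqrt(0.09 + 0.04) = 0.361 at P = 0.20.
- Period-adjusted estimate = average of the two order means, with variance (s²/4) x (1/n1 + 1/n2) and 28 df. It is free of P.

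**Bias.** At 15/15: zero. At 18/12: 0.10 x 6/30 = 0.02, or 0.20 x 6/30 = 0.04. At 20/10: 0.10 x 10/30 = 0.033, or 0.20 x 10/30 = 0.067.

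**Power and type I error, one group, s = 0.30** (simulation for the unadjusted test, noncentral t for adjusted power; where two values are given they are for P = 0.10 / 0.20):

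| Orders | Quantity | Without period | With period |
|---|---|---|---|
| 15/15 | power at 0.22 | 93% / 87% | 94.4% |
| 15/15 | type I error | 1.8% / 0.8% | 2.5% |
| 18/12 | power, shift opposing the drug effect | 87% / 67% | 93.5% |
| 18/12 | power, shift adding to it | 97% / 97% | 93.5% |
| 18/12 | type I error | 2.6% / 2.5% | 2.5% |
| 20/10 | type I error | 4% / 7% | 2.5% |

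With s = 0.424 at 15/15, power is 66% or 59% without the term and 68% with it.

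**How likely is imbalance?** The protocol says only that order uses a procedure similar to that for group, where "Males and females will be randomized without replacement across a block of 60 codes". For 30 participants, the probability of 18/12 or worse is 0.196 if one list of 30/30 codes is used, 0.294 if two sex-specific lists each supply 15, and 0.362 under simple randomisation. For 20/10 or worse it is 0.019, 0.058 and 0.099. These schemes are assumptions.

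**Which period term?** A single period effect shared by both groups is not enough if the shift differs by group. With orders 20/10 in both groups and an assumed shift of 0.20 in one group only, a common period term leaves type I error at 3.9% for that group's contrast and 6.6% for group x drug; with no term the latter is about 5.5%. Adding group x period brings both to about 2.5%.

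**The case against.** The strongest counter-argument is the within-session control. Protocol section 9 (Sessions 6 & 7) recalibrates the leg raise each session and takes a pre-drug leg raise at rest before the infusion, and the SAP names two leg raises. If the rest-versus-manipulation factor compares the pre-drug leg raise with the one during meditation, a shift common to both cancels, and only a shift in their difference survives. The wording allows this reading, which is why P is defined above as what is left after that control. It may be small.

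There is weak indirect evidence in the same direction. The protocol reports the same root mean square errors, 0.23 and 0.30, for its planning models with and without session order. A shift of 0.20 would move 0.23 to about sqrt(0.0529 + 0.20²/4) = 0.25. The text may have been carried over, or the pilot data may differ, so this settles little.

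It is also fair that the plan intends equal orders, that the equal-order test is conservative, and that in the SAP the paired tests follow only a significant interaction. The type I errors above are therefore those of a standalone contrast and not of the whole procedure.

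A reader might infer from the missing term that the drug contrast is biased or its type I error inflated. The documents do not support that: bias needs both a residual shift and unequal orders, and at 18/12 type I error is still nominal. Nor does session order in one planning model show that the sponsor found a period effect.

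What stands is that a randomised, known factor is left out. Conservatism is also not neutral here, because one of the hypotheses is that naloxone does not reverse mindfulness analgesia, and extra error makes that non-significant result easier to obtain.

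**Conclusion.** The omission is real and minor. At equal orders it costs precision only: about 1 to 2 points of power for an assumed residual shift of 0.10, and 7 to 8 points for 0.20 (one group of 30, SD of difference 0.30). Bias of P x (n1 - n2)/n arises only with unequal orders. Type I error rises noticeably only at splits near 20/10, whose probability is about 0.02 to 0.10 under the allocation schemes assumed. All these sizes rest on an assumed P, since the documents give none. The case for change is that the adjustment is nearly free, not that the planned test is invalid.

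**What to change.** In the protocol (section 9, Data Analyses and Interpretation) and the SAP (Statistical Analysis Plan paragraph), keep the planned outcome and the within-session pre-drug control, and add period (Session 6 versus 7) and group x period as fixed effects. If rest versus manipulation stays as a factor, add the corresponding period x manipulation terms. Code period 0 for Session 1, -0.5 for Session 6 and +0.5 for Session 7, so that baseline can stay in the three-level model. Take the within-group naloxone-saline contrasts and the group x drug interaction from this model, in place of unadjusted paired tests.

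The cost is wording and one or two degrees of freedom; drug order is already assigned. If there is no period effect, two groups of 30 with SD 0.30, effect 0.22 and alpha 0.025 give (noncentral t, 58 df without the terms and 56 with them):

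- 15/15 in both groups: within-group power 95.4% either way, and interaction power 70.4% either way.
- 20/10 in both groups: within-group power falls from 95.4% to 92.8%, and interaction power from 70.4% to 64.7%.

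Separately, Sessions 6 & 7 in protocol section 9 assigns 30 participants per group to each order. Read literally this is 60 per group and does not fit the stated total of 30 per group. It may mean 30 per order across both groups; the text should be reconciled.
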